3.3 Secondary Study Endpoints

- 1) Determine ECG changes and incidence of arrhythmias after consumption of Adderall compared to baseline ECG
- 2) Determine if consumption of a dose of Adderall is associated with altered neurohormonal and cardiovascular activation, assessed by measurements of biomarkers, such as catecholamines before and after Adderall/placebo intake
- 3) Determine if taking Adderall induces orthostatic changes
- 4) Assess baroreflex sensitivity (paced breathing) before and after Adderall vs placebo intake
- 5) Determine the effect of Adderall on cardiovascular hemodynamics during stress conditions including mental stress (arrhythmics), physical stress (sustained hand grip) and pain stress (cold pressor stress) as compared to measurements at rest
- 6) Determine the changes in heart function and brachial artery reactivity after Adderall intake using ultrasound
- 7) Determine the changes in appetite and food consumption after Adderall vs placebo
- 8) Determine the prevalence of stimulant medication use, history of weight changes and dietary habits among healthy adults (utilizing standard questionnaires).

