5.9.4 Return or Destruction of Study Drug

Study drug will be supplied by the Mayo Clinic pharmacy on a one-to-one basis, rather than batches. In this respect we do not anticipate to have drugs remaining or drugs to return. At the completion of the study, there will be a final reconciliation of drug provided by the Mayo Clinic Pharmacy, drug dispensed, drug returns, and drug remaining. This reconciliation will be logged on the drug reconciliation form, signed and dated. Any discrepancies noted will be documented and investigated, prior to return or destruction of unused study drug. Drug destroyed on site will be documented in the study files.

6 Study Procedures

6.1 Visit 1

Two CRTU visits - minimum 5 days apart, maximum 3 months apart.

CRTU Day # 1

1. Subjects report to SMH CRTU at the already pre-scheduled appointment time. Participants should not eat at least 4 hours prior to coming to CRTU. Participant is reminded to avoid all stimulants including caffeine and alcohol 24 hours prior to the study.
2. CRTU personnel informs study personnel when the subject arrives at the CRTU.
3. Study personnel explain the research study to the participant and obtain written informed consent.
4. CRTU personnel will obtain height and weight of the participant.
5. CRTU personnel performs urine pregnancy test as needed (Urine collection #1). If the participant is pregnant, then the participant is unable to participate in the study, and will receive \$25.00 for their time. In all participants at least 100 ml of urine may be collected for future biomarker analysis at baseline
6. Study personnel verbally ask and record the responses to Cardiovascular Research Data Sheet including anthropometrics and bioimpedance measurements.

7. Participant will be asked to fill out the following questionnaires on a Mayo laptop or on paper. Some of these questionnaires may be administered more than once: Stimulant Intake Questionnaire, Berlin Questionnaire, Breakfast Questionnaire, Food Scale, Food Intake Questionnaire, Adult ADHD Self Report Checklist, Symptoms Questionnaire, Sleepiness Scale.
8. CRTU Staff will insert peripheral intravenous line into the forearm and blood draw #1 will be obtained after at least 30 minutes of supine resting.
9. Study personnel will obtain BP and HR measurements in supine position. Measurements will be taken every 1-3 minutes throughout the study.
10. Study personnel will be obtaining 12-lead ECG recording throughout the study.

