11. Study personnel will perform paced breathing test, details described in the IRB Protocol. Breathing will be measured by elastic bands around the chest and abdomen.
12. Baseline endothelial function test will be performed by the study team.
13. Study personnel will perform orthostatic BP and HR measurements.
14. Study personnel blinded to the study will give the participant the study drug vs placebo drug with a glass of water, according to the randomized, double-blind, placebo-control crossover design of this study.
15. Study subject will be asked to rest in sedentary or recumbent position for 3 hours.
16. CRTU Staff will do blood draw #2 after 30 minutes of supine resting, 3 hours after intake of active drug/placebo drug.
17. The 12-lead ECG recording continues on.
18. Study personnel will perform post-intervention paced breathing test, details described in the IRB Protocol. Breathing will be measured by elastic bands around the chest and abdomen.
19. Post intervention endothelial function test will be performed by the study team.
20. Post intervention ultrasound of the heart may be performed by the study team or echo lab personnel.
21. Study personnel will perform orthostatic BP and HR measurements.

22. Study personnel will describe the series of stress tests that will follow and BP, HR, ECG measurements will continue through the stress tests.
23. Study personnel will perform series of stress tests (physical, mental, and cold stress), details described in the IRB Protocol. During the stress tests continuous BP, HR and 12-lead ECG data will be recorded and will continue to be recorded the recovery time periods.

Participants will be allowed to eat, selecting meals from a prepared menu.

24. Study subjects will be scheduled a follow up appointment in the CRTU to be done within 2 months (minimum 5 days apart) but at the same time of the day; and will be dismissed home for the day.

6.2 Visit 2

CRTU Day # 2

1. Subjects report to SMH CRTU at the already pre-scheduled appointment time. Participants should not eat at least 4 hours prior to coming to CRTU. Participant is reminded to avoid all stimulants including caffeine and alcohol 24 hours prior to the study.
2. CRTU personnel informs study personnel when the subject arrives at the CRTU.
3. Study personnel explain the research plan for day #2 and answers any questions the participant may have.

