9. Food/Diet monitoring: At the end of the study day, subjects will be given a menu of food options and will be asked to select the foods they wish to eat. The menu will be consistent for all subjects and include low fat, high fiber foods as well as high fat, high sugar and high sodium foods. The food will be weighed by specially trained staff from the team of dieticians. Subjects will be allowed to order and consume as much food as desired. When done eating, the tray of food, including leftovers, will be removed. We will record their appetite level, selection of foods, and actual amount of consumption of food. Leftovers will be weighed and the nutrient analysis will be calculated for the actual food intake using ProNutra software. The analysis will include Calories, Protein, Fat, Carbohydrate, Fiber, and Sodium as well as total weight of the food and beverages served. A consistent menu will be offered and the same procedure will be followed after subjects receive placebo vs. Adderall.
10. Urine sample: At least 100 ml of urine will be collected for future biomarker analysis with each urine collection.

7 Statistical Plan

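### The food-intake weight outcome is weight served, not weight eaten, and pre-visit eating is only partly standardised between the two study days

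*Combined protocol and SAP*

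**What the plan says.** Secondary endpoint 7 (Section 3.3, repeated in Section 7.1) reads: "Determine the changes in appetite and food consumption after Adderall vs placebo". Section 1.1 hypothesises acute appetite suppression.

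The measurement is described in Section 6, in item 9 (Food/Diet monitoring) of the procedure list after Visit 2. Subjects choose freely from a fixed menu at the end of the day, with no limit on quantity, and the food is weighed. Staff note appetite, the choices made and how much was really eaten. The outputs are given in one sentence: "The analysis will include Calories, Protein, Fat, Carbohydrate, Fiber, and Sodium as well as total weight of the food and beverages served". The nutrient items named there rest on intake, since the text just before them states: "Leftovers will be weighed and the nutrient analysis will be calculated for the actual food intake using ProNutra software". Menu and method are to be identical on the drug day and the placebo day.

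Sections 6.1 and 6.2 give the same pre-visit rule for both days: "Participants should not eat at least 4 hours prior to coming to CRTU". Subjects are also reminded to "avoid all stimulants including caffeine and alcohol 24 hours prior to the study", and the second visit is booked for the same time of day. The Day 1 questionnaire list includes a Breakfast Questionnaire, a Food Scale and a Food Intake Questionnaire. Of these, the Day 2 list names only the Food Scale. Both lists say that some questionnaires may be given more than once.

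**The concern.** There are two separate issues, both affecting the same secondary endpoint.

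The first is the definition of the weight outcome. Calories and nutrients are calculated on what was eaten, but the weight item that follows them is what was served. Served weight does not subtract leftovers. It responds to the drug only through ordering, so it is not a measure of consumption. If the wording is literal, one listed output does not measure the endpoint it sits under. If it is loose, the analyst must choose between served and eaten weight without guidance from the plan.

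The second is comparability of the two days. A minimum fast lets the same subject arrive after different fasting lengths and different last meals. Blood pressure and heart rate have a pre-dose reading on each day, and the planned group-by-time interaction uses it. The test meal happens once per day, after dosing, so intake has no same-day baseline. Any difference between the days in prior eating that affects intake goes straight into the drug-placebo difference. The visits may be months apart, so a difference not recorded at the time is hard to recover. At stake is precision on endpoint 7.

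**Working it through.** The documents give no sample size, standard deviation or effect for food intake. The power statement in Section 7.1 concerns blood pressure, heart rate and similar variables, so there is no stated figure to reproduce here.

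**Served against eaten weight.** For each day let S be weight served and L weight left, so eaten weight is E = S − L. The drug-placebo differences then satisfy

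ΔE = ΔS − ΔL.

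Served weight captures ΔS only. It agrees with eaten weight when leftovers do not change (ΔL = 0) and shows nothing when orders do not change (ΔS = 0). As an illustration, assume 1000 g served on both days and 10% left on placebo:

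- 25% left on Adderall: ΔS = 0 g; eaten 750 g against 900 g, a fall of 150 g (150/900 = 17%).
- 40% left on Adderall: ΔS = 0 g; eaten 600 g against 900 g, a fall of 300 g (300/900 = 33%).

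Equal orders are the extreme case. In both examples the recorded amount consumed shows the fall, and the intake-based nutrient measures reflect what was eaten.

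**What is standardised before the meal.**

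| Feature | Both days? |
|---|---|
| Minimum 4 h fast before arrival | Yes |
| No stimulants or alcohol for 24 h | Yes |
| Same time of day | Yes |
| Same menu and meal procedure | Yes |
| Same last meal | Not requested |
| Same fasting length | Not requested |
| Time of last intake recorded | Not clearly required on Day 2 |

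Section 3.1 gives sessions of 6 to 8 hours. If the meal closes the session, the minimum time since last eating is about 4 + 6 = 10 h to 4 + 8 = 12 h. A difference of *h* hours in fasting at arrival is still *h* hours at the meal, but on a base of at least 10 to 12 h and not 4 h. The effect is therefore probably diluted, but it is not removed.

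**What the noise could cost (assumption only).** Suppose matching pre-visit eating removed a share f of the variance of the within-subject drug-placebo difference. The detectable difference would be multiplied by √(1 − f). Take a paired t test, two-sided 0.05, with 80% power before matching. For n = 30 that corresponds to a difference of 0.529 standard deviations of the within-subject difference. After matching, the same difference is 0.529/√(1 − f) of the smaller standard deviation:

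| f (assumed) | √(1 − f) | Standardised difference after matching | Power |
|---|---|---|---|
| 0.10 | 0.95 | 0.558 | 84% |
| 0.25 | 0.87 | 0.611 | 90% |
| 0.50 | 0.71 | 0.748 | 98% |

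Starting from 80% power with n = 25 (the approximate enrolment in Section 3.1; detectable difference 0.584), the powers are the same to the nearest percent. No figure in the documents says where f lies.

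**The case against.** The case on the other side is substantial, and most of it stands.

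*Served weight is one item among several.* It is listed beside six intake-based measures, the protocol records the amount actually consumed, and eaten weight follows by subtraction. A reader might infer that the trial could miss appetite suppression altogether. The documents do not support that: the intake-based measures would still be there to show it. Because subjects order freely, the amount ordered may itself fall with appetite, so served weight is informative about selection. The word may also simply be careless. What remains is that the listed output, read literally, is not consumption.

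*Pre-visit eating is already partly controlled.* A reader might infer that it is neither controlled nor recorded. That goes too far. The fast, the abstinence rule and the fixed time of day are real controls, and the long session dilutes differences at arrival. The Breakfast and Food Intake forms are not in the documents. They may record habits for endpoint 8, in which case a single administration is reasonable. The Food Scale is used on both days, its content is also unseen, and repeat administration is permitted. What can be said is that nothing requests matching and no listed Day 2 item clearly requires recording.

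*Bias.* A reader might also infer a biased comparison. Order is randomised and blinded, so unequal fasting is not systematically tied to drug or placebo. It adds variance.

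*Scale.* This is one of eight secondary endpoints in a self-described pilot. That limits the importance of the point but does not argue against a nearly free correction.

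**Conclusion.** The point holds in limited form and is minor. The listed weight outcome measures ordering, although the endpoint is consumption. The loss is recoverable from data already planned, and the calorie and nutrient measures are unaffected. Pre-visit eating is only partly standardised, so the single end-of-day meal outcome carries avoidable within-subject noise.

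The 150 to 300 g contrast rests on assumed serving and leftover amounts. The gain from 80% to between 84% and 98% power rests on assumed variance shares of 10% to 50%. Neither is an estimate for this trial. The conclusion on recording rests on the questionnaire lists alone, because the forms cannot be inspected. The validity of the primary blood pressure and heart rate comparison is not in question.

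**What to change.** 1. In the Food/Diet monitoring item, define the weight outcome as weight consumed, that is, served minus weighed leftovers, and state that undrunk beverages count among the leftovers. Keep served weight only if it is labelled as a measure of food selection.
2. In Sections 6.1 and 6.2, ask subjects to repeat the same last meal and the same fasting length before both visits, within the protocol's existing fasting minimum.
3. Record the time of last intake on both days.

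The first change is essentially wording, because food and leftovers are already weighed. The second and third cost one instruction to subjects, a small added burden on them, and one data field per visit. No new equipment or procedure is needed.

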7.1 Sample Size Determination

Anticipating to study 30 subjects, we will have 80% power to detect a significant increase in the blood parameters (i.e. BP, HR etc.) for the study drug as compared to the placebo drug, with a 2-sided significance level of 0.05. Specifically, we are powered to detect an effect size of 0.80, which is a difference in the means between the different types of drugs (study vs. placebo) that is 80% of the standard deviation. For example, we are powered to detect an increase of 5% in the blood parameters for the study drug vs. only a 1% increase for the placebo drug (4% difference), assuming a standard deviation of 5% (effect size = 0.80).

Data Analysis Plan: Plan is to analyze data using two-way analysis of variance (ANOVA) for repeated-measures with time (before vs after drug intake) as the within factor and group (study drug vs placebo drug) as the between factor. The key variable will be the group-by-time interaction. Differences in hemodynamics (BP, HR) before and after consumption of a drug will be determined by repeated measures ANOVA. Student *t* test (paired or unpaired) will be used for between group comparisons with respect to change in given variable. $P < 0.05$ will be considered statistically significant. Data will be expressed as mean \pm SEM.

Endpoints:

Primary Endpoint:

- 1) Determine the hemodynamic changes (magnitude of BP and HR response) in healthy adults after taking one dose of prescription medication Adderall 25 mg orally, one time, and compare these responses to those after a placebo pill

Secondary Endpoint:

- 1) Determine ECG changes and incidence of arrhythmias after consumption of Adderall compared to baseline ECG
- 2) Determine if consumption of a dose of Adderall is associated with altered neurohormonal and cardiovascular activation, assessed by measurements of biomarkers, such as catecholamines before and after Adderall/placebo intake
- 3) Determine if taking Adderall induces orthostatic changes
- 4) Assess baroreflex sensitivity (paced breathing) before and after Adderall vs placebo intake
- 5) Determine the effect of Adderall on cardiovascular hemodynamics during stress conditions including mental stress (arrhythmics), physical stress (sustained hand grip) and pain stress (cold pressor stress) as compared to measurements at rest
- 6) Determine the changes in heart function and brachial artery reactivity after Adderall intake using an ultrasound
- 7) Determine the changes in appetite and food consumption after Adderall vs placebo
- 8) Determine the prevalence of stimulant medication use, history of weight changes and dietary habits among healthy adults (utilizing standard questionnaires).

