11	ETHICAL CONSIDERATIONS	36
12	STUDY FINANCES	36
12.1	FUNDING SOURCE	36
12.2	CONFLICT OF INTEREST	36
12.3	SUBJECT STIPENDS OR PAYMENTS	376
13	PUBLICATION PLAN	376
14	REFERENCES	38

List of Abbreviations

LIST OF ABBREVIATIONS

BP	Blood Pressure
CRTU	Clinical Research and Trials Unit
DBP	Diastolic Blood Pressure
DSMP	Data and Safety Monitoring Plan
ECG	Electrocardiography
FMD	Flow-Mediated Vasodilation
FTP	File Transfer Protocol
HIPAA	Health Insurance Portability and Accountability Act
HR	Heart Rate
IND	Investigational New Drug Application
IRB	Institutional Review Board
PHI	Protected Health Information
SBP	Systolic Blood Pressure
UPIRTSO	Unanticipated Problems Involving Risk to Subjects or Others

Study Summary

Title	Cardiovascular Effects of Adderall in Healthy Young Adults. A Randomized Clinical Trial.
Running Title	Cardiovascular Effects of Adderall in Healthy Young Adults.
Protocol Number	16-004743
Phase	Phase I
Methodology	Double blind, randomized, placebo controlled, cross-over study
Overall Study Duration	2016-2019
Subject Participation Duration	2 study day visits
Single or Multi-Site	Single-site
Objectives	To investigate the blood pressure and heart rate response to consumption of a dose of Adderall in healthy young subjects
Number of Subjects	30
Diagnosis and Main Inclusion Criteria	
 1) Adults 18 years of age and older 2) Healthy subjects without known cardiovascular disease, thyroid disease or documented mental health illness 3) Subjects who are on no medications that directly interact with the study drug 4) Subjects with no prior history of regular amphetamine use, and non-prescription stimulants 5) Nonsmokers
Study Product, Dose, Route, Regimen	Adderall 25 mg PO once
Duration of Administration	1 time dose of Adderall and 1 time dose of placebo drug
Reference therapy	Placebo drug
Statistical Methodology	Student t test will be used for between group comparisons. Data will be also analyzed using two-way analysis of variance for repeated-measures.

1 Introduction

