3.1 General Design

The cardiovascular effects of Adderall, prescription medication often abused by students for non-medical purposes, are not well understood. This is a pilot study to investigate the cardiovascular and metabolic response to taking an oral dose of Adderall (25 mg) by healthy adults. Subjects will be studied using a randomized, double-blind, placebo-controlled, crossover design with two separate experimental sessions: Adderall and placebo pill; studies will be performed on 2 separate study days, each study lasting from 6-8 hours.

[figure not shown]
Active drug: Oral Generic Adderall: total of 25 mg dose. This dose will be compounded by Pharmacy. The compounded dose will contain: [dextroamphetamine sulfate 6.25 mg, dextroamphetamine saccharate 6.25 mg, amphetamine aspartate monohydrate 6.25 mg, amphetamine sulfate 6.25 mg (equivalent to amphetamine base 15.73 mg)].

Placebo drug: Placebo designed by CRTU Research Pharmacist team

Adderall and placebo drug will be prepared by research pharmacists in similar capsule form. Placebo pill is carefully designed by our team of CRTU Research Pharmacists to match the prescription medication, Adderall. Both drugs will be given in an identical manner so that participants and study investigators are not aware of which drug is being administered. Subjects will remain unaware of the nature of the drug administered on each study day throughout the study. Each experimental session (Adderall and placebo pill) will be conducted using the same protocol, in a random order.

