5.3 Method for Assigning Subjects to Treatment Groups

The proposed research study is a randomized, double-blind, placebo-controlled clinical trial. The randomization list will be computer generated. We will utilize a randomized block design, with a block size of 6, considering enrolling 30 subjects, each completing two study days. This assures balance between the treatment arms after each group of 6 subjects. Subjects and study personnel will be blinded to the nature of the pill administered on each study day.

Randomization will be performed by CTSA statistician. De-identified coded spreadsheet will be provided to the research pharmacist who will be distributing the drug/placebo.

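### The stated 80% power for effect size 0.80 with 30 subjects does not reproduce for the crossover: on the natural reading it is understated, its SD and test are undefined, and section 3.1 gives a different N

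*Combined protocol and SAP*

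**What the plan says.** Section 7.1 gives the power claim: "Anticipating to study 30 subjects, we will have 80% power to detect a significant increase in the blood parameters", at a two-sided significance level of 0.05. It continues: "Specifically, we are powered to detect an effect size of 0.80, which is a difference in the means between the different types of drugs", expressed as 80% of an SD that is not identified. The worked example sets a 5% increase on drug against "only a 1% increase for the placebo drug (4% difference), assuming a standard deviation of 5% (effect size = 0.80".

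The design in section 3.1 is a crossover: "Subjects will be studied using a randomized, double-blind, placebo-controlled, crossover design with two separate experimental sessions". Section 5.3 plans the randomisation in blocks of 6, "considering enrolling 30 subjects, each completing two study days", and adds: "This assures balance between the treatment arms after each group of 6 subjects".

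The analysis text is written differently. Section 7.1, and section 7.2 under both the primary hypothesis and secondary hypothesis 1, enter drug versus placebo as a between-group factor in a repeated-measures ANOVA. All three places leave the t test open: "paired or unpaired) will be used for between group comparisons with respect to change in given variable". The Study Summary says only: "Student t test will be used for between group comparisons".

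On sample size, section 3.1 expects to enrol roughly 25 subjects. The Study Summary and sections 4.1, 5.3, 7.1 and 7.2 all give 30. No dropout rate is stated. Section 7.2 expects little missing data, and section 4.4.1 keeps enrolment open until the intended number has completed.

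**The concern.** Section 7.1 is the plan's only numerical justification for the sample size, and it cannot be checked against the design. A crossover comparison rests on the SD of the within-subject difference between drug and placebo. The plan does not say whether 5% is that SD, the SD of percent change in one session, or something else. It gives no within-subject correlation and does not name the test behind the 80%.

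What is at stake is whether the reader learns the effect the trial can detect. If the calculation belongs to a different design, the stated detectable effect of 0.80 SD is not the one that 30 crossover subjects provide. The two values of N add a smaller question: at what number does enrolment end, and does that number count subjects enrolled or subjects completing both days?

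**Working it through.** **Inputs from section 7.1:** difference 5% − 1% = 4 points; SD 5%; n = 30; two-sided alpha 0.05; claimed power 80%. The plan's ratio is correct: 4/5 = 0.80. **Assumed, because the plan gives none:** the within-subject correlation rho between the two sessions' changes, shown at 0, 0.3 and 0.5.

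**Method:** exact noncentral-t power.
- Paired: noncentrality = dz × √n, df = n − 1, where dz is the mean difference divided by the SD of the within-subject difference.
- Unpaired: noncentrality = d × √(n per group / 2), df = 2 × (n per group) − 2.

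**Step 1. Where does 80% at 0.80 appear?**
- Unpaired, 25 per group: 0.80 × √12.5 = 2.83, power 79.1%.
- Unpaired, 26 per group: 0.80 × √13 = 2.88, power 80.7%.
- Unpaired, 30 per group: 0.80 × √15 = 3.10, power 86.1%.
- Paired, 14 subjects: 79.0%; 15 subjects: 82.1%.

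The stated 30 gives 80% neither as 30 pairs nor as 30 per group.

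**Step 2. Paired test, 5% taken as the SD of the within-subject difference.** dz = 0.80.
- n = 30: 0.80 × √30 = 4.38, df 29, power 98.8% (also 98.8% with 28 df, allowing for a period effect).
- n = 25: 0.80 × √25 = 4.00, df 24, power 97.0%.

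**Step 3. Paired test, 5% taken as the SD of percent change in one session.** SD of the difference = 5 × √(2(1 − rho)), so dz = 0.80/√(2(1 − rho)).

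| rho (assumed) | dz | Power, n = 30 | Power, n = 25 |
|---|---|---|---|
| 0 | 0.566 | 85.0% | 77.5% |
| 0.3 | 0.676 | 94.7% | 90.0% |
| 0.5 | 0.800 | 98.8% | 97.0% |

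On this reading, power equals 80% at rho of about −0.14 for n = 30 and about 0.06 for n = 25. At rho = 0 the smallest n reaching 80% is 27 (80.8%; 26 gives 79.2%), so 30 recruited would tolerate 3 losses.

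**Step 4. Effect detectable with 80% power by a paired test.** dz = 0.53 at n = 30 and 0.58 at n = 25. In points at n = 30, using the unrounded 0.529:
- 5% is the SD of the difference: 0.529 × 5 = 2.65.
- 5% is the per-session SD of change: 0.529 × 5 × √(2(1 − rho)) = 3.74, 3.13 or 2.65 at rho 0, 0.3 or 0.5.

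**Step 5. Sample size against the blocks.** 30/6 = 5 complete blocks; 25 = 4 × 6 + 1, which leaves a block incomplete.

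**The case against.** The strongest reply is that the error, if it is one, is on the safe side. On the natural reading, 30 completers with rho of 0 or more give at least 85% power, so the promised 80% is met and N need not change. The trial also calls itself a pilot. All of this stands, and it limits the severity. It does not make the statement correct, because the detectable effect is misdescribed and the reader cannot tell which SD to use.

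A second reply is that the calculation fits the model as written: with drug as a between-group factor, a two-group formula is what one would use. That is fair, and it shows that the analysis wording has to change along with the power paragraph. It does not rescue the figure, since 30 per group gives 86.1%.

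A third is that section 3.1 is a loose expectation while the target accrual, randomisation and power sections all say 30. That also largely stands. The mismatch is a matter of consistency with little effect on power.

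A reader might go further and infer that the trial is underpowered. Treating 5% as the SD of a single raw measurement, with four uncorrelated measurements per subject, gives 56.3% at n = 30; splitting 30 into 15 versus 15 gives 56.2%. The documents do not support either reading. The example attaches the SD to percent increases, and each subject completes both days. Zero correlation among repeated readings on one person is also an extreme assumption: even on the raw-measurement reading, power passes 80% once the common correlation exceeds about 0.43, and is 85.0% at 0.5.

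**Conclusion.** The point holds as a misstated and under-specified power claim, of minor to moderate severity. For the planned crossover with 30 completers, the stated 80% is too low on the natural reading: 98.8% if 5% is the SD of the within-subject difference, and 85.0% to 98.8% if it is the per-session SD of change with rho from 0 to 0.5. These figures rest on the paired test and on values of rho that the documents do not supply.

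The match with an unpaired calculation at 25 to 26 per group is suggestive, and consistent with the between-group wording of the ANOVA, but it remains an inference. Going from 30 to 25 or 26 would mean a loss of 5/30 = 17% or 4/30 = 13%, and no such allowance is written anywhere.

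The 25 in section 3.1 does conflict with 30 elsewhere. At 25, power falls below 80% only if 5% is a per-session SD and rho is below about 0.06 (77.5% at rho 0); it is 90% or more at rho of 0.3 or above.

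**What to change.** 1. **Section 7.1, power.** Restate it on the paired comparison, for example: *With 30 completers, a two-sided 0.05 paired t test on the within-subject difference (drug minus placebo) in change from baseline has 80% power for 0.53 SD of that difference.* Identify the 5% SD, state any assumed correlation, and give the matching detectable difference from Step 4. If the 80% came from a two-group calculation with a dropout allowance, say so and state the allowance.
2. **Sections 7.1 and 7.2 (primary hypothesis and secondary hypothesis 1), analysis.** Make drug a within-subject factor and specify the paired t test only. Align the Study Summary. Changing 7.1 alone would leave the power basis contradicting the analysis.
3. **Sample size.** Correct section 3.1 to 30, which is five complete blocks of 6, and say whether 30 means subjects enrolled or completers, so that the enrolment rule in 4.4.1 has a definite end point.

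The cost is wording in several sections, including the named primary test. No additional subjects are needed.
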